8.3.7 Guidelines for reporting product complaints

Any defect in the IMP must be reported as soon as possible by the Investigator to the monitoring team that will complete a product complaint form within required timelines.

Appropriate information (eg, samples, labels or documents like pictures or photocopies) related to product identification and to the potential deficiencies may need to be gathered. The Investigator will assess whether or not the quality issue has to be reported together with an AE or SAE.

8.4 PHARMACOKINETICS

8.4.1 Sampling times

The sampling times for blood collection can be found in the SoA ([Section 1.3](#))

8.4.2 Sample handling procedure

Special procedures for collection, storage, and shipment are provided in the laboratory manual.

8.4.3 Bioanalytical methods

Details of bioanalytical methods can be found in the laboratory manual.

8.4.4 Pharmacokinetic parameters

Plasma concentrations of BIVV020 will be obtained. This data may be included in a population PK analysis.

[figure not shown]
Pharmacokinetic samples could be used for testing analytical method performance such as comparability and incurred sample reproducibility.

8.5 GENETICS AND/OR PHARMACOGENOMICS

Participants may provide consent for future research to be performed utilizing their samples. This may include DNA analysis (See [Section 8.9](#) and [Section 10.5](#)).

8.6 BIOMARKERS

- Collection of biological samples for biomarker research is also part of this study. The following samples for biomarker research are required and will be collected from all participants in this study as specified in the SoA ([Section 1.3](#)):

- Samples will be tested to evaluate their association with the observed clinical responses.
- In addition, samples will be stored and analysis may be performed on additional biomarkers related to the complement pathway to evaluate their association with observed clinical responses.
- Samples may be used for research to develop methods, assays, prognostics and/or companion diagnostics related to the mechanism of action of BIVV020.
- Samples collected for biomarker analyses and their derivatives will be stored for a period of up to 5 years after last patient last visit for potential re-analyses.

8.7 IMMUNOGENICITY ASSESSMENTS

Antibodies to BIVV020 will be evaluated in plasma samples collected from all participants according to the SoA ([Section 1.3](#)). Additionally, plasma samples should also be collected at the final visit from participants who discontinued study intervention or were withdrawn from the study. These samples will be tested by the Sponsor or Sponsor's designee.

Plasma samples will be screened for antibodies binding to BIVV020 and the titer of confirmed positive samples will be reported. Other analyses may be performed to verify the stability of antibodies to BIVV020 and/or further characterize the immunogenicity of BIVV020.

The detection and characterization of antibodies to BIVV020 will be performed using a validated assay method by or under the supervision of the Sponsor. All samples collected for detection of antibodies to study intervention will also be evaluated for BIVV020 plasma concentration to enable interpretation of the antibody data. Antibodies may be further characterized and/or evaluated for their ability to neutralize the activity of the study intervention(s). Samples may be stored for a maximum of 5 years (or according to local regulations) following the last participant's last visit, at a facility selected by the Sponsor to enable further analysis of immune responses to BIVV020.

8.8 HEALTH ECONOMICS OR MEDICAL RESOURCE UTILIZATION AND HEALTH ECONOMICS

Health economics or medical resource utilization and health economics parameters are not evaluated in this study.

8.9 USE OF BIOLOGICAL SAMPLES AND DATA FOR FUTURE RESEARCH

Future research may help further the understanding of disease subtypes, disease biology, related conditions, drug response and toxicity, and can help identify new drug targets or biomarkers that predict participant response to treatment. Therefore, data and biological samples will be stored and used for future research when consented to by participants (see [Section 10.1.3](#)) unless prohibited by local laws or IRBs/IECs (in such case, consent for future use of sample will not be included in the local ICF).

For participants who consent to the storage and use of their data and remaining and/or extra clinical samples, data and samples may be used after the study ends for future research related either to the drug, the mechanism of action, and the disease or its associated conditions. Such research may include, but is not limited to, performing assessments on DNA, RNA, proteins or metabolites. If future research on genetic material is performed, this will also be limited to the purpose of addressing research questions related to the drug, the mechanism of action, the disease or its associated conditions.

In the event future research is conducted for other purposes, the study participants will be informed of those purposes and will be given means to object to those research projects.

Data and samples will be used in compliance with the information provided to participants in the ICF Part 2 (future research).

All study participant data and samples will be coded such that no participant direct identifiers will be linked to them. Coded data and samples may be transferred to a Sponsor site (or a subcontractor site), which may be located outside of the country where the study is conducted. The Sponsor adopts safeguards for protecting participant confidentiality and personal data (see [Section 10.1.4](#)).

The samples will be stored for a maximum of 15 years after the end of the study. Any samples remaining at the end of retention period will be destroyed. If a participant requests destruction of his/her samples before the end of the retention period, the Investigator must notify the Sponsor (or its contract organization) in writing. In such case, samples will be destroyed and related coded data will be anonymized unless otherwise required by applicable laws.

Study participant coded data will be stored for future research for up to 25 years after the end of the study. If data are still considered of important scientific value after this period, coded data already available will be anonymized unless otherwise required by applicable laws (the same will apply to the data of a study participant who has requested the destruction of his/her samples).

A participant's coded data sets provided to researchers for a specific research project will be available to the researchers for a maximum of 2 years after the end of their specific project (end of project is defined by publication of the results or finalization of the future research project report).

9 STATISTICAL CONSIDERATIONS

9.1 SAMPLE SIZE DETERMINATION

Approximately 12 participants will be enrolled to receive the study intervention. Since there is no statistical hypothesis to be tested, the sample size is not determined statistically.

9.2 POPULATIONS FOR ANALYSES

The following populations for analyses are defined:

Table 5 - Populations for analyses

Population	Description
Screened	All participants who signed the informed consent form (ICF).
Enrolled	All participants from the screened population who receive at least 1 dose (full or partial) of study intervention.
Intention to Treat (ITT)	All participants who receive at least 1 dose (full or partial) of study intervention.
Safety	All participants who receive at least 1 dose (full or partial) of study intervention.
Pharmacokinetic (PK)	All participants who receive at least 1 dose (full or partial) of study intervention with sufficient sample data.
Pharmacodynamic (PD)	All participants who receive at least 1 dose (full or partial) of study intervention with sufficient sample data to assess PD parameters.
PK/PD	All enrolled participants in the PK population with at least 1 time-matched PK/PD parameter.

9.3 STATISTICAL ANALYSES

The Statistical Analysis Plan (SAP) will include a more technical and detailed description of the statistical analyses described in this section. This section is a summary of the planned statistical analyses of the most important endpoints including primary and key secondary endpoints.

9.3.1 General considerations

- Common definitions of baseline.
- General methods (eg, how the continuous variables will be summarized).

The baseline value is defined as the last non-missing assessment before the first dose of study drug.

Unless otherwise specified, analyses will be performed based on the populations described above; safety analysis will be performed based on the safety population; PK, PD, and PK/PD analyses will be performed using the respective populations as defined in [Section 9.2](#).

The observation period will be divided into 3 segments:

- The **pre-treatment period** is defined as the period from enrollment up to the first dose of study intervention. Demographics, baseline disease characteristics, medical history, and prior therapy including prior ITP therapy use will be summarized based on data collected in this period.
- The **treatment-emergent (TE) period (or the study treatment period) for efficacy** and exposure analysis is defined as the period from the first study intervention administration to the last study intervention administration +7 days.
- The **safety analysis period** is defined as the period from the first study intervention administration to the EOS visit. Safety summaries will be based on this period.

9.3.2 Primary endpoint

The primary endpoint is described in [Section 3](#).

The number and proportion of participants meeting the responder criteria will be presented; the 95% confidence interval of the proportion of responders will be estimated using Clopper-Pearson method. Missing data will not be imputed in the statistical analysis. If a patient discontinues study treatment prior to Week 3, the patient will be considered as a non-responder. If a patient discontinues the study treatment after Week 3 and prior to Week 24, his or her responder status will be assessed using the available data between Week 3 and Week 24.

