3 OBJECTIVES AND ENDPOINTS

Table 2 - Objectives and endpoints

Objectives	Endpoints
Primary 
To evaluate the effect of BIVV020 on the durability of platelet response in participants with persistent/chronic immune thrombocytopenia (ITP)	
Naïve participants: Proportion of participants with a platelet count $\geq 50 \times 10^9/L$ at $\geq 50\%$ of scheduled visits, or for participants with baseline platelet count $< 15 \times 10^9/L$, a $\geq 20 \times 10^9/L$ increase in platelet count from baseline at $\geq 50\%$ of scheduled visits, without receiving rescue ITP therapy, as assessed from Week 3 to Week 24.Participants who previously received sutmilimab: Proportion of participants with maintenance of platelet count $\geq 30 \times 10^9/L$ at $\geq 50\%$ of scheduled visits, without receiving rescue ITP therapy, as assessed from Week 3 to Week 24.
Secondary 
To assess the safety and tolerability of BIVV020To assess the pharmacokinetics (PK) of BIVV020To assess the response rate of treatment with BIVV020To assess the time to responseTo assess the effect of treatment with BIVV020 on the requirement for rescue ITP therapyTo assess the immunogenicity of BIVV020	
Standard clinical and laboratory parameters and adverse eventsPlasma concentrations of BIVV020Response rate at Weeks 24 and 52, defined as a platelet count $\geq 50 \times 10^9/L$ and a greater than 2-fold increase from baseline, measured on 2 occasions at least 7 days apart, with the absence of bleeding (bleeding is defined as bleeding with a score ≥ 2 on the WHO bleeding scale), and the lack of combination ITP therapy during this period.Time from baseline to first platelet response, defined as greater than or equal to each of the following values: $50 \times 10^9/L$ and $100 \times 10^9/L$ (confirmed by 2 measurements at least 7 days apart)Proportion of participants who did not require rescue therapy for an acute episode of thrombocytopenia after Week 3Incidence and titer (if relevant) of anti-BIVV020 antibodies

Objectives	Endpoints
Exploratory	

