7 DISCONTINUATION OF STUDY INTERVENTION AND PARTICIPANT DISCONTINUATION/WITHDRAWAL

7.1 DISCONTINUATION OF STUDY INTERVENTION

7.1.1 Permanent discontinuation

In rare instances, it may be necessary for a participant to permanently/definitely discontinue the study intervention. If this occurs, a new participant may be enrolled to replace the one who was discontinued, unless the permanent discontinuation was due to a BIVV020-related adverse reaction or safety concern.

The Investigator/Sponsor must permanently discontinue dosing with BIVV020 in a participant if any of the following participant-level stopping rules are met:

- Pregnancy in a participant while receiving study drug.
- Change in compliance with inclusion/exclusion criteria that is clinically relevant and affects patient's safety.
- Intake of non-permitted concomitant medications that might affect participant's safety or study assessments/objectives.
- An allergic reaction, including an anaphylactic reaction, in association with BIVV020 administration.
- SLE or any other immune complex disease.
- Meningococcal infection.
- Occurrence of AEs that, in the opinion of Investigator/Sponsor, may jeopardize patient safety or data integrity. These include, but are not limited to, abnormal liver tests and abnormal QTc, meeting the stopping criteria (see [Section 7.1.2](#), [Section 7.1.3](#), [Appendix 6](#), [Section 10.6](#)).
- Lack of efficacy (see [Section 7.1.4](#)).
- Participant misses more than 3 consecutive doses of BIVV020 without Investigator approval. If a participant misses 3 consecutive doses and the Investigator believes the participant should remain in the study, a protocol for BIVV020 re-initiation may be considered, in consultation with the Sponsor.

Handling of participants after permanent intervention discontinuation

If study intervention is definitively discontinued, the participant should continue to be followed for an additional 22 weeks. The procedures listed for the EOS visit as per the SoA should be performed at the final visit.

All cases of definitive intervention discontinuation must be recorded by the Investigator in the appropriate pages of the electronic case report form (eCRF) when considered as confirmed.

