#### *Observation period*

The observation period will be divided into 3 segments:

- The **pre-treatment period (or the screening period)** is defined as the period from the time of the signing of the informed consent form (ICF) to the first IMP administration.
- The **on-treatment period** is defined as the period from the first IMP administration to the last IMP administration +7 days.
- The **post-treatment period** is defined as the period after the on-treatment period.

The **treatment-emergent** (TE) period includes both on-treatment period and post-treatment period.

Analyses of safety will be based on the treatment-emergent period.

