### **4.3 PRIMARY ENDPOINT(S) ANALYSIS**

The primary endpoint is the proportions of participants who met the following criteria:

1. For naïve participants,
  - a platelet count  $\geq 50 \times 10^9/L$  OR
  - a  $\geq 20 \times 10^9/L$  increase from baseline if baseline platelet count  $< 15 \times 10^9/L$  at  $\geq 50\%$  of scheduled visits from Week 3 to Week 24.

For switchers, a platelet count  $\geq 30 \times 10^9/L$  at  $\geq 50\%$  of scheduled visits from Week 3 to Week 24.

2. No concomitant ITP therapy from Week 3 to Week 24.

Concomitant medications are defined in [Section 5.3](#). The ITP therapies will be identified by the Sanofi coding group, reviewed by medical, and defined in the programming specifications. The ITP therapies include corticosteroids, thrombopoietin receptor agonists, intravenous immunoglobulin, anti-D immunoglobulin, rituximab, fostamatinib, immunosuppressants (azathioprine, cyclosporin A, mycophenolate mofetil), cyclophosphamide, dapsone, danazol.

The response rate will be summarized for naïve participants, switchers, and total for the ITT along with the 95% exact Clopper-Pearson Confidence Interval (CI).

Platelet counts will be summarized by visit. These plots will also be provided:

- Individual platelet count profile: line plot of platelet count by visit for each participant

- Spaghetti plot platelet count by participant
- Median platelet count/change from baseline with by visit

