### ***Prior or concomitant medications***

All medications will be coded using the World Health Organization-drug dictionary (WHO-DD) using the version currently in effect at Sanofi at the time of database lock.

- Prior medications are those the participant used prior to first IMP intake. Prior medications can be discontinued before first administration or can be ongoing during treatment period.
- Concomitant medications are any interventions received by the participant concomitantly to the IMP during the on-treatment period.
- Post-treatment medications are those the participant took in the period running from the end of the concomitant medications period up to the end of the study.
- A given medication can be classified as a prior medication and/or as a concomitant medication and/or as post-treatment medication. If it cannot be determined whether a given medication was taken prior or concomitantly or post, it will be considered as prior, concomitant, and post-treatment medication.

The prior, concomitant, and post-treatment non-ITP medications will be summarized for the ITT population, by anatomic and therapeutic level. The summaries will be sorted by decreasing frequency of anatomic category (ATC) based on incidence in intervention group. Therapeutic classes are sorted by decreasing frequency within each anatomic class. In case of equal frequency, alphabetical order will be used. Participants will be counted once in each ATC category (anatomic or therapeutic) linked to the medication.

Prior ITP, concomitant non-rescue ITP, and concomitant rescue ITP therapies/medications will be summarized separately by the ATC level 4 chemical class and medication name. All ITP therapies will be listed with rescue ITP therapies flagged.

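### For participants who stop between Week 3 and Week 24 the denominator is not stated, so the durability endpoint can be read as met on one or two platelet counts

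*Protocol*

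**What the plan says.** **Endpoint.** Protocol section 3 and SAP 4.3 require the platelet threshold at 50% or more "of scheduled visits from Week 3 to Week 24". The objective is durability of response.

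**Stopping.** Under protocol 9.3.2, stopping before Week 3 is non-response. For stopping after Week 3 and before Week 24, "his or her responder status will be assessed using the available data between Week 3 and Week 24". Missing data are not imputed. SAP 4.3 has no rule for stopping or for missing counts, and SAP 5.2 declares no changes to the protocol's analyses. SAP 5.4 labels an empty analysis window as missing and does not say what that does to the denominator.

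**Period of use.** The protocol's efficacy period (9.3.1) "is defined as the period from the first study intervention administration to the last study intervention administration +7 days".

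**Follow-up.** After permanent discontinuation (protocol 7.1.1), "the participant should continue to be followed for an additional 22 weeks", with End of Study procedures at the final visit. Section 7.2 adds an early discontinuation visit, where possible, for someone leaving the study.

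**Therapy criterion.** The protocol's endpoint reads "without receiving rescue ITP therapy, as assessed from Week 3 to Week 24". SAP 4.3 has "No concomitant ITP therapy from Week 3 to Week 24" and points to SAP 5.3, where "Concomitant medications are any interventions received by the participant concomitantly to the IMP during the on-treatment period". The on-treatment period in SAP 4.1 "is defined as the period from the first IMP administration to the last IMP administration +7 days".

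**Visit windows.** SAP Table 6 targets Week 8 at Day 57, Week 10 at Day 80, Week 12 at Day 85, Week 24 at Day 169 and Week 32 at Day 171.

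**The concern.** A participant who responds early, relapses and is stopped for lack of efficacy (protocol 7.1.4) is a clear case of a response that did not last. If the later visits leave the denominator, that participant can still be counted as a durable responder, provided no disqualifying ITP therapy was taken. Participants who never respond fail under either rule, so the issue is confined to early responders who stop.

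The study has about 12 participants, no control group and no hypothesis test. The reported proportion and its interval are the efficacy result, and SAP 4.3 also gives them separately for naïve participants and switchers. Two programmers could both follow the text and classify the same participant differently.

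The SAP deals with the same kind of stopping elsewhere. In the time-to-response analysis (SAP 4.4), non-responders who stop for an adverse event or lack of response are censored at Week 57, not when they stop, so they stay in the risk set to the end. The primary endpoint has no corresponding rule.

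**Working it through.** The plan gives no figure to reproduce: the sample size of about 12 is stated not to be statistically determined.

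**1. Scheduled counts, Week 3 to Week 24.** SAP 1.1 says counts are collected at on-site visits. With the visit weeks in the protocol's Schedule of Activities, these are Weeks 3, 4, 5, 6, 8, 10, 12, 16, 20 and 24, so N = 10. In the text copy of that schedule, where marks may have been lost, Day 22 (Week 3) and Day 36 (Week 5) are blank in both the platelet and hematology rows, which gives N = 8.

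**2. Counts needed.** With k counts available at stopping, the available-data reading needs ceil(k/2) of k. The fixed denominator needs ceil(N/2) of N: 5 of 10, or 4 of 8. The largest share of the full schedule that a stopper can reach is k/N.

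| Schedule | Last count | k | Needed on available data | Largest share of schedule |
|---|---|---|---|---|
| N = 10 | Week 3 | 1 | 1 | 10% |
| | Week 4 | 2 | 1 | 20% |
| | Week 5 | 3 | 2 | 30% |
| | Week 6 | 4 | 2 | 40% |
| | Week 8 | 5 | 3 | 50% |
| N = 8 | Week 4 | 1 | 1 | 12.5% |
| | Week 6 | 2 | 1 | 25% |
| | Week 8 | 3 | 2 | 37.5% |
| | Week 10 | 4 | 2 | 50% |

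Example with N = 10: threshold met at Weeks 3 and 4, not met at Weeks 5 and 6, then stopped for relapse. Available data give 2/4 = 50%, a responder. The full schedule gives 2/10 = 20%, a non-responder.

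**3. Effect on the reported rate.** The documents give no dropout rate, so assume 0, 1 or 2 such participants.
- Of 12: 0, 1/12 = 8.3 or 2/12 = 16.7 points.
- If each is replaced (allowed by protocol 7.1.1 unless the stop is for a drug-related reaction or safety concern) and stays in the ITT population of exposed participants (SAP Table 2): 0, 1/13 = 7.7 or 2/14 = 14.3 points.
- In a group of 6 (up to 6 switchers are planned): one participant is 1/6 = 16.7 points.

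Clopper-Pearson 95% limits for x of n are the 0.025 quantile of Beta(x, n−x+1) and the 0.975 quantile of Beta(x+1, n−x). For illustration:
- 5/12 = 41.7% (15.2 to 72.3) against 4/12 = 33.3% (9.9 to 65.1)
- 3/6 = 50.0% (11.8 to 88.2) against 2/6 = 33.3% (4.3 to 77.7)

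**4. SAP Table 6.** Week w falls on Day 7w + 1, which reproduces Week 8 = 57, Week 12 = 85 and Week 24 = 169.
- Week 10 = 7 × 10 + 1 = 71; Table 6 has 80. An on-time count (Days 69 to 73) misses the window of Days 78 to 82. Where these windows assign the counts, it becomes missing. A completer then needs 5 of 9 usable counts (55.6%), or 4 of 7 (57.1%) when N = 8.
- Week 32 = 7 × 32 + 1 = 225; Table 6 has 171. Its window (Days 167 to 175) overlaps Week 24 (Days 165 to 173). Counts on Days 171, 172 and 173 are 0, 1 and 2 days from the Week 32 target and 2, 3 and 4 days from the Week 24 target.

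**5. Therapy after stopping.** The endpoint wording runs to Week 24. The SAP 5.3 definition ends 7 days after the last dose. With a last dose on Day 22, the second ends on Day 29, so therapy started between Day 30 and Week 24 disqualifies under one and may not under the other. The scope differs too: the protocol names rescue therapy, whereas the SAP names any concomitant ITP therapy.

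**The case against.** **The endpoint may already fix the denominator.** It speaks of scheduled visits. The sentence on available data, and the absence of imputation, can be read as saying only which counts can pass; a missing count is then simply not a pass. A reader might infer that the plan requires visits after stopping to be dropped. The documents do not support that. The separate non-responder rule for stopping before Week 3 points towards the lenient reading. The efficacy period and the follow-up schedule govern which data exist or are used, not how many visits were scheduled. Both readings stay open, and that is the defect.

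**Counts after stopping may exist.** One might infer from protocol 7.1.1 that nothing falls inside the window after stopping. Section 7.2 also provides an early discontinuation visit with End of Study procedures, which include a platelet count, and leaves other key visits to discussion. The End of Study visit has a window of ±14 days: for a last dose on Day 22 it is nominally Day 22 + 154 = 176, so Days 162 to 190. Such visits could add a count or so, but they do not settle the denominator.

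**The affected set is small.** Protocol 7.1.1 calls permanent discontinuation rare and 7.2 calls withdrawal uncommon. As worded, SAP 4.3 disqualifies any concomitant ITP therapy, which narrows the set further. The individual platelet plots and the disposition table would show such a case. All this stands, but the reported rate would still include it.

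**The therapy passages can be reconciled.** Reading SAP 4.3 and 5.3 as a flat contradiction goes too far: the criterion may mean the overlap of the two periods. It is an ambiguity of scope.

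**Table 6 is written for by-visit analyses.** Its use for the responder endpoint is not stated, so that effect is conditional.

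**Conclusion.** The gap is real and should be closed. For participants who stop between Week 3 and Week 24, neither document fixes the denominator or a minimum number of counts. On the available-data reading, one or two counts are enough for durable response if the last count is by Week 6 (10-count schedule) or by Week 10 (8-count schedule).

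The size rests on assumed numbers of early responders who stop: nothing if there are none, 8.3 points per participant among 12, and 16.7 points in a group of 6. The intervals overlap widely, so what changes is the point estimate. A reader might infer a demonstrated bias in the response rate; the documents support only a rule left open, with an effect that may turn out to be zero.

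The therapy criterion is unclear both in period and in which therapies count. Separately, the Week 10 and Week 32 targets in SAP Table 6 are wrong as written, by the table's own day numbering.

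**What to change.** - **Schedule and windows.** Set the Table 6 targets for Week 10 to Day 71 and Week 32 to Day 225. Reconcile the platelet row of the Schedule of Activities with SAP 1.1.
- **Denominator.** In SAP 4.3 and protocol 9.3.2, define it as all Week 3 to Week 24 visits with a scheduled platelet count. Score visits after permanent treatment discontinuation as not met. Report the available-data version as a sensitivity analysis.
- **Counts missed on treatment.** State the rule and show the result both ways, since treating them as failures is debatable when a visit is lost for an unrelated reason such as site disruption.
- **Therapy criterion.** Reconcile protocol section 3, SAP 4.3 and SAP 5.3 on which therapies count and whether the period runs to Week 24 regardless of stopping. Add a rule for unknown therapy status after study withdrawal.

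The cost is a few sentences and two table entries, best settled before results are known. The denominator rule needs no new data. It is a different estimand, because stopping is treated as failure from that point on; relative to the available-data reading it can only lower the rate or leave it unchanged. The downside is that a participant who stops for an unrelated reason may be scored a non-responder, which the sensitivity analysis would show.
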